6.4. Analysis Sets

Three analysis sets will be used.

Screening Analysis Set: all subjects who give written informed consent and have entered screening. The Screening Analysis Set consists of two mutually exclusive subgroups:

- subjects who were not randomized at completion of screening, generally due to failure of one or more of the study entry criteria (i.e., the inclusion/exclusion criteria) and
- subjects who were randomized at completion of screening

Safety Analysis Set: all randomized subjects who take at least one dose of study drug. Subjects will be evaluated by their randomized treatment arm ('intent-to-treat' analysis) unless otherwise specified. The Safety Analysis Set will be the primary set for safety summaries. Safety summaries may also be provided based on the treatment actually received.

All Randomized Analysis Set: all randomized subjects. Subjects will be evaluated by their randomized treatment arm ('intent-to-treat' analysis) unless otherwise specified. The All Randomized Analysis Set will be the primary set for efficacy analyses.

Achieve will approve the list of subjects to be excluded from the Safety and All Randomized analysis sets after database lock. Achieve must approve this list before any analysis to be performed.

6.5. Key Study Endpoints

Achieve has identified the following endpoints as key study endpoints:

- Percent of expected cigarettes smoked (primary efficacy endpoint, see [Section 4.1.1](#))
- Abstinence from Week 5 to Week 8 (other efficacy endpoint, see [Section 4.1.2](#))
- Adverse events (serious adverse events, adverse events that resulted in dose reduction or discontinuation of study drug, all adverse events)

- Exposure to study drug, including study drug compliance

6.6. Sensitivity Analyses

Sensitivity analyses will include the assessment of the contribution of interaction terms and effect modification analyses.

Unless otherwise indicated, the sensitivity and effect modifier analyses will be conducted by an independent statistician () who will document the results of those analyses in a statistical report that will be included as an appendix to the clinical study report.

The sensitivity analyses outlined in this Statistical Analysis Plan will be performed for both the primary efficacy endpoint (see [Section 10.1.2](#)) and the abstinence from Week 5 to Week 8 endpoint (see [Section 10.2.2](#)).

6.7. Interactions and Covariates

Interactions: Assessment of the effect of interaction between treatment (1.5 mg cytisine, 3.0 mg cytisine, placebo) and the BMI stratification factor (18.5 to <25 kg/m²; 25 to <30 kg/m²; 30 to <35 kg/m²) will be included in the sensitivity analyses.

Covariates: Baseline cigarettes smoked, defined as the average number of cigarettes smoked daily over the 7-day screening period.

7. SUBJECT DISPOSITION

The number of subjects who were screened, failed screening, randomized and treated will be summarized overall. The reason for failing screening will also be summarized.

The number of subjects screened, randomized, treated, discontinuing and completing study drug, completing and withdrawing from the study, as well as the number of subjects in each analysis set will be summarized for each treatment arm. In addition, the number of subjects screened, randomized and treated will be summarized by investigational site for each treatment arm.

For subjects who discontinued study drug, the reasons for discontinuation (e.g. adverse event, withdrawal by subject, physician decision) will be summarized for each treatment arm. The list of subjects who discontinued study drug will be reported, along with the reason for discontinuation.

For subjects who did not complete the study, the reasons for withdrawal (e.g. adverse event, withdrawal by subject, physician decision) will be summarized for each treatment arm. The list of subjects who withdrew from the study will be reported, along with the reason for withdrawal. Reasons will also be reported for why subjects were excluded from each analysis set. The list of subjects who are excluded from the Safety Analysis Set (subjects randomized but who never

took any study drug before discontinuing from the study) will be reported only if those subjects had safety information collected.

Attendance at each study visit will be reported with the number and percentage of subjects who attended each visit (i.e. Screening #1, Screening #2, Randomization, Treatment Day 1, etc.). Similarly, the last study visit attended will be reported with the number and percentage of subjects having their last study visit at Week 8, Week 7, etc.

The number and percentage of subjects who completed the Treatment Period (i.e., attended the Day 27 EOT) and Follow-up Assessment Period (i.e., attended the Week 8 visit) will be reported.

A Kaplan-Meier figure will be produced by treatment arm of time to last recorded data related to the abstinence endpoints (i.e., time from date of randomization to date of last smoking cessation data recorded at or prior to the Week 8 visit). Smoking cessation data includes the self-reports of cigarette smoking [number of cigarettes smoked in previous 24 hours, whether any cigarettes were smoked since the last clinic visit (yes, no) or over the past 7 days (yes, no)] and expired CO levels.

7.1. Protocol Deviations

Protocol deviations will be reported as outlined in the ACH-CYT-09 Monitoring Plan and documented in the CRF. Each deviation will be classified as either “major” or “minor”. Major deviations were defined in the monitoring plan as those requiring direct/immediate escalation to the Sponsor/Medical Monitor in order to determine if the subject can continue with his/her study participation. These included deviations in the following categories:

- Inadequate informed consent procedures,
- Violations of inclusion/exclusion criteria,
- Errors in randomization/stratification,
- Missing results from screening assessments used for determining subject eligibility.

The number and percentage of subjects with at least one deviation (major or minor) and with at least one major deviation will be summarized by treatment arm. For major deviations, the number and percentage of subjects with each type of deviation (e.g., informed consent, inclusion/exclusion criteria, etc.) will be summarized by treatment arm.

8. DEMOGRAPHIC AND OTHER BASELINE CHARACTERISTICS

Demographic and other baseline characteristics will be listed and summarized.

8.1. Demographics

Demographic data (gender, age, race, ethnicity, body weight, height, and BMI) will be summarized for each of the subgroups in the Screening Set, and overall.

Demographic data will also be summarized by treatment arm and overall for both the All Randomized Analysis Set and the Safety Analysis Set.

8.2. Medical and Psychiatric History

A medical and psychiatric history summary will be provided for the All Randomized Analysis Set. The number and percentage of subjects with events will be summarized for each treatment arm by MedDRA SOC and preferred term. Multiple occurrences of the same event within a subject will be counted only once.

8.3. Prior Medications

Per protocol, concomitant medications will be recorded beginning at the Screening #1 (SV1) visit. Prior medications are defined as medications with a stop date prior to the first dose of study drug. Prior medications will be summarized for the All Randomized Analysis Set. The number and percentage of subjects with each prior medication will be summarized for each treatment arm by highest available Anatomical Therapeutic Chemical (ATC) class and preferred name. Multiple occurrences of the same medication within a subject will be counted only once.

8.4. Smoking History

At SV1 the following subject-reported smoking history variables will be summarized by treatment arm.

- Duration of smoking (years)
- Average number of cigarettes the subject reported smoking per day over the past 30 days
- Number (%) of subjects who attempted to quit in the past
- Number of previous quit attempts
- Time from last quit attempt to date of SV1 visit

In addition, the number (%) of subjects reporting past use of various smoking cessation treatments will be summarized for both the most recent quit attempt and all quit attempts. For each of these summaries, multiple occurrences of the same treatment within a subject will be counted only once.

8.5. Baseline Smoking and Nicotine Testing

The following baseline data related to smoking will be summarized by treatment arm:

- Average number of cigarettes smoked per day over 7 consecutive days, as reported in the subject diary
- Expired CO (ppm) at SV1
- Expired CO (ppm) at Day 0
- Nicotine metabolism ratio (NMR) at SV1. NMR will be derived as the ratio of the results for 3-hydroxycotinine (3-OH cotinine) and cotinine (i.e., 3-OH cotinine / cotinine).

8.6. Baseline Questionnaires

Subjects will complete the Suicidal Behaviors Questionnaire – Revised (SBQ-R) and Hospital Anxiety and Depression (HADS) questionnaires at SV1 and the Fagerstrom Test of Nicotine Dependence (FTND), Self-efficacy Questionnaire (SEQ-12), Tobacco Craving Questionnaire (TCQ) and Alcohol Use Questionnaire at Day 0, prior to randomization. The following scores will be derived and summarized at baseline by treatment arm:

- SBQ-R: total score
- HADS: scores for depression and anxiety (see Appendix 5, study protocol)
- FTND: total score
- SEQ-12: internal stimuli score (items 1-6), external stimuli score (items 7-12) and total score (items 1-12)
- TCQ: scores for emotionality, expectancy, compulsivity and purposefulness (see Appendix 4, study protocol), as well as a total score.

In addition, the number and percentage of subjects with each item response on the baseline Alcohol Use Questionnaire will be summarized by treatment arm.

8.7. Other Baseline Characteristics

Vital signs (body temperature, heart rate, and systolic and diastolic blood pressure) will be assessed at two timepoints prior to randomization: SV1 and Day 0. Baseline vital signs will be summarized by treatment arm.

Serum chemistry and hematology testing will be performed at SV1. Baseline laboratory test results will be summarized by treatment arm. Separate summaries will be provided for hematology tests (hemoglobin, red blood cells, white blood cells, neutrophils, lymphocytes, monocytes, eosinophils, basophils and platelets), serum chemistry tests (total protein, albumin, total bilirubin, aspartate aminotransferase (ALT), alanine aminotransferase (AST), alkaline phosphatase, glucose, sodium, potassium, calcium, creatinine and urea) and creatinine-clearance.

A 12-lead ECG will be performed at SV1. Baseline ECG findings (normal, abnormal – not clinically significant, abnormal – clinically significant) will be summarized by treatment arm.

9. EXPOSURE TO STUDY TREATMENT

Study treatment consisted of administration of study drug in combination with behavioral support.

9.1. Duration of Study Drug Treatment

The time (days) from randomization to first dose of study drug will be derived and summarized by treatment arm for the Safety Analysis Set.

Duration of study drug treatment (days) will be calculated as date of last dose of study drug minus date of first dose of study drug + 1. Duration of study drug treatment will be summarized by treatment arm for the Safety Analysis Set. The number (%) of subjects who had duration of 25 days will be summarized by treatment arm.

9.2. Study Drug Compliance

A dose of study drug consisted of 2 tablets. Subjects assigned to the 25-day commercial schedule will be prescribed a total of 100 doses of study drug. Subjects assigned to the tid schedule will be prescribed a total of 69 doses.

Each dose of study drug taken by the subject will be recorded in a subject diary. For each dosing day (Day 1 to Day 25), the dosing date will be recorded as well as each of the dosing times and, for each dosing time, whether the dose was taken by the subject or missed. The total dose of study drug taken over the 25-day treatment period will be derived for each subject.

The following variables will be summarized by treatment arm for the Safety Analysis Set:

- total dose of study drug,
- total number of missed doses,
- percentage of doses missed: $(\# \text{ missed doses} / \# \text{ doses prescribed}) * 100$
- study drug compliance: $[(\# \text{ doses prescribed} - \# \text{ missed doses}) / \# \text{ doses prescribed}] * 100$.

Compliance with study drug will be summarized both as a continuous variable and as a categorical variable (<80%, 80-<90%, 90-<100%, 100%). In addition to summary tables, details of study drug administration and compliance will be listed. The listing will include the total number of doses taken by the subject, total number of doses missed, percentage of doses missed, and percentage of doses taken (i.e. compliance with study drug) in addition to the details of each dose (date of administration, time of administration and whether dose was taken or missed).

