
Rationale: (-)-Cytisine is a naturally occurring plant-based alkaloid, isolated from seeds of Cytisus laburnum (Golden chain), that is believed to reduce the severity of nicotine withdrawal symptoms while inhibiting nicotine's effects by targeting nicotinic acetylcholine receptors (nAChRs) in the brain. Cytisine administered at the 1.5 mg dose has been used as a smoking cessation drug since the 1960's in Central and Eastern European countries. Previous studies dating from decades ago to support use in Central and Eastern Europe, and more recent studies conducted to Good Clinical Practice (GCP), have shown that cytisine can be effective in helping smokers to stop smoking. The titration schedule for the commercial product comprises a gradual reduction in the number of tablets per day from 6 tablets to 1 tablet over a 25-day treatment period. However, no studies are available evaluating how alternative dose exposure and administration impacts outcomes within the treatment period. The intent of this Phase 2b trial is to test the logistics and planned Phase 3 procedures, including compliance using various blister packaging, as well as the general effectiveness of cytisine treatment and the intended behavioral support in overall smoking cessation rates for subsequent Phase 3 sample size determinations.
 
This Phase 2b trial is being conducted at sites within the United States (US) to evaluate cytisine dosage and administration schedules within a 25-day treatment period. Study arms will consist of the commercial 1.5 mg dose/titration schedule that is marketed in European countries, a higher dose of 3.0 mg following the marketed titration schedule, 1.5 mg and 3.0 mg doses using an initial three times a day (tid) schedule and respective placebo arms for either schedule. The study will evaluate efficacy based on the overall reduction in the number of cigarettes smoked during the various study treatment dosing/schedules as well as evaluate general compliance and safety profiles compared to the respective placebo arms (i.e. the marketed titration schedule or a simplified tid schedule). Results will also be used to aid defining Phase 3 sample size calculations when using the planned behavioral support and timing of study evaluations for the Phase 3 primary endpoint of abstinence from Week 5 to Week 8 post-randomization.

Objectives:

Efficacy Objectives:

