2.2. Treatment Schedules

For the 25-day commercial titration schedule, study drug will be administered according to the following schedule:

Treatment Day	Daily Administration	Approximate Interval
1-3	6 times daily	2 hours
4-12	5 times daily	2.5 hours
13-16	4 times daily	3 hours
17-20	3 times daily	4-5 hours
21-24	2 times daily	6 hours
25	1 time only	-

For the tid schedule, study drug will be administered according to the following schedule:

Treatment Day	Daily Administration	Approximate Interval
1-20	3 times daily	4-5 hours
21-24	2 times daily	6 hours
25	1 time only	-

All subjects will receive 2 tablets for each dose according to their randomization arm.

Subjects that work overnight will potentially be taking their daily administered dose over two calendar days. This is accounted for in the CRF and the date of their first dose taken will be recorded as the dosing start date.

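### As written, the SAP's study drug compliance formula credits unrecorded doses as taken, unless the CRF or programming forces them to missed

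*SAP*

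**What the plan says.** SAP 9.2 fixes the denominator by schedule: "Subjects assigned to the 25-day commercial schedule will be prescribed a total of 100 doses of study drug" and "Subjects assigned to the tid schedule will be prescribed a total of 69 doses". For each dosing day from Day 1 to Day 25 the diary holds the date, the dosing times and, "for each dosing time, whether the dose was taken by the subject or missed". Compliance is then 100 times (prescribed minus missed) divided by prescribed. It is summarized by arm in the Safety Analysis Set, both as a continuous variable and in four categories (below 80%, 80 to below 90%, 90 to below 100%, and 100%). The accompanying listing gives the number of doses taken and describes the compliance figure as the "percentage of doses taken (i.e. compliance with study drug".

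SAP 6.5 names as a key study endpoint: "Exposure to study drug, including study drug compliance". The protocol synopsis (Rationale) gives compliance a central place: "The intent of this Phase 2b trial is to test the logistics and planned Phase 3 procedures, including compliance using various blister packaging". SAP 4.1.2 and 10.2.6 relate the percent of study drug taken to the efficacy endpoints.

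Nothing visible says how to count a prescribed dose that has no entry. SAP 6.3 treats dropouts in general terms and SAP 6.3.1 covers missing dates only.

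**The concern.** The formula starts from full credit and deducts only what someone recorded as missed. A blank dosing time is deducted by nobody, so absence of data raises the score. The result then disagrees with the label in the same section, because prescribed minus missed equals taken only when every one of the 100 or 69 slots carries an entry.

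The SAP's two other compliance measures run the other way. Behavioral support compliance (SAP 9.3) is sessions received over sessions planned, and diary compliance (SAP 10.1.3) is days entered over days expected. In both, missing data lower the score.

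Two uses are at stake. The first is the by-arm compliance summary: if active and placebo arms within a schedule lose subjects at different rates, the comparison shifts in favour of the arm with more loss. The second is the exploratory analysis of percent of drug taken against outcome. SAP 4.1.2 classes subjects with insufficient data as failures for abstinence and for initial quit, so an early loss could enter as a fully compliant failure, which would weaken any true association.

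**Working it through.** **1. Reproduce the plan's denominators** from the schedules in SAP 2.2.

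- Commercial: 3×6 + 9×5 + 4×4 + 4×3 + 4×2 + 1×1 = 18 + 45 + 16 + 12 + 8 + 1 = 100.
- tid: 20×3 + 4×2 + 1×1 = 60 + 8 + 1 = 69.

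Both agree with SAP 9.2.

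**2. Compare two formulas when records stop early.** Let P be doses prescribed, M doses recorded as missed and K doses recorded as taken.

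- SAP formula: 100 × (P − M) / P.
- Taken-based formula: 100 × K / P.

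They are equal when K + M = P, that is, when every slot is recorded. Otherwise they differ by 100 × (unrecorded doses) / P.

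Suppose every dose up to the last recorded day was taken, and later slots are blank (M = 0):

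| Records end after | Commercial, taken-based | tid, taken-based | SAP formula, both |
|---|---|---|---|
| Day 6 | 33/100 = 33.0% | 18/69 = 26.1% | 100% |
| Day 10 | (3×6 + 7×5)/100 = 53.0% | 30/69 = 43.5% | 100% |
| Day 12 | 63/100 = 63.0% | 36/69 = 52.2% | 100% |
| Day 20 | 91/100 = 91.0% | 60/69 = 87.0% | 100% |

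With records ending after Day 6 and two doses recorded as missed, the SAP formula gives 98/100 = 98.0% or 67/69 = 97.1%. The taken-based figures are 31/100 = 31.0% or 16/69 = 23.2%. The subject moves from the lowest compliance category to the second highest.

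A diary gap on Days 8–10 alone leaves 15 commercial or 9 tid doses unrecorded. The taken-based figures are 85/100 = 85.0% and 60/69 = 87.0%; the SAP formula gives 100% for both.

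**3. Arm level.** The documents give no dropout or diary-loss rate, so these are assumptions. If a fraction f of an arm has records ending after Day 10 with no missed entry, the arm mean exceeds the taken-based mean by f × (100 − taken-based %):

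- f = 10%, commercial: 0.10 × (100 − 53) = 4.7 points.
- f = 10%, tid: 0.10 × (100 − 43.5) = 5.65, about 5.7 points.

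Under the same assumption, the active-minus-placebo difference is biased by the difference in f between the two arms times 47 points (commercial) or 56.5 points (tid). Equal loss raises both means and leaves the difference alone. A loss rate 10 percentage points higher in one arm shifts the difference by 4.7 or about 5.7 points.

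As a second illustration, let the other subjects average 95% and let records stop after Day 6 for 5%, 10% or 20% of an arm:

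| Share stopping after Day 6 | SAP mean | Taken-based, commercial | Taken-based, tid |
|---|---|---|---|
| 5% | 95.2% | 91.9% | 91.6% |
| 10% | 95.5% | 88.8% | 88.1% |
| 20% | 96.0% | 82.6% | 81.2% |

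The SAP mean rises as loss rises.

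**The case against.** The strongest reply is that SAP 9.2 describes a two-way status for every scheduled dosing time through Day 25. If that is how the data are held, no slot is blank, taken plus missed equals prescribed, and the two formulas are identical. The label in the listing suggests that this was the intent. The eCRF and its completion guidelines, which SAP 1 lists among the documents reviewed, are not available here, and the table and listing shells are blacked out, so a derivation rule may exist out of sight. This stands: a reader might infer that the SAP has decided to count unrecorded doses as taken, but it nowhere says so. The formula has that effect only where slots are left blank.

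A reader might also infer that everyone who stops treatment early is scored as fully compliant. The protocol does not support that. Subjects who discontinue drug continue all remaining evaluations (8.3.1), and those who withdraw while on drug are asked to complete the end-of-treatment assessments (8.3.2). Staff reconcile packs against the diary, recording tablets taken and missed (11), and document diary entries on the CRF at each visit (12.2.5). The exposure is therefore mainly withdrawals, losses to follow-up and lost diaries.

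A third tempting inference is that the flaw undermines a planned comparison of titration with tid on compliance. The protocol synopsis and section 5 set compliance against the respective placebo arms, within schedule. The between-schedule comparisons in Protocol 6.2 and SAP 3.2 belong to the other efficacy objectives, and compliance is not among them.

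Finally, duration of treatment (SAP 9.1), doses taken (SAP 9.2) and discontinuations with reasons (SAP 7) are also reported, so heavy early stopping would be visible beside the compliance figure. That helps a careful reader but does not correct the compliance figure itself or its use in the exploratory analysis.

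**Conclusion.** The point holds conditionally. On the only meaning the SAP gives to a missed dose, a prescribed dose with no entry stays in the numerator. For an affected subject the gap is large: 100% against 53% (commercial) or 43.5% (tid) when records end after Day 10, assuming no missed entries and no later reconciliation. The conclusion rests on some slots being left blank and on no CRF or programming rule setting blanks to missed; the visible documents neither confirm nor exclude such a rule. The trial-level size cannot be stated without dropout and diary-loss rates.

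What is affected is a named key study endpoint, the active-versus-placebo compliance summaries within each schedule, and the exploratory relation of percent of drug taken to outcome. The primary efficacy endpoint does not use the formula. The text should be changed rather than left to interpretation, because the corrected formula gives the same answer if recording is in fact complete.

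**What to change.** In SAP 9.2, define compliance as 100 × (doses recorded as taken) / (doses prescribed). Where the diary is missing, use the returned blister-pack counts, which Protocol 9.8 and 11 already provide for. Class any dose still unrecorded as not taken, and report the number of such doses by arm on its own line. Apply the same rule to the percentage of doses missed and to the four compliance categories.

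The cost is a short SAP edit and one extra table row. The downside is that a subject who took doses but lost both diary and packs is scored low; the line for unrecorded doses shows how often that could be happening.
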